- T. Pre-dose and post-dose sampling will be performed for PK, dTT, and aPTT/ECT only for patients on the dabigatran etexilate arm. Pre-dose sampling should occur immediately before intake of dabigatran etexilate, post-dose sampling should be performed at 2 hours post-dabigatran etexilate dose (this time point corresponds to the approximately peak dabigatran plasma concentration). Pre-dose sampling is mandatory for all dabigatran etexilate assigned patients. The post-dose sample is optional for dabigatran etexilate patients.
- U. Compliance for dabigatran etexilate and SOC will be calculated by the investigator or designee preferably based on actual medication count (or alternatively based on daily medication intake logs which will be completed by the patient or if appropriate by the parent/legal guardian). Counting the returned medication is the preferred calculation method to assess compliance.
- V. This assessment will be completed by the patient (if old enough per investigator judgment) or by the parent / legal guardian. The aim of this evaluation will be to obtain additional information about the experience of taking dabigatran etexilate as capsules, pellets or oral liquid formulation (reconstituted with flavoured or unflavoured solvent).
- W. Dabigatran etexilate or SOC (not supplied in the study) may be re-dispensed as needed in appropriate cases (e.g. dabigatran etexilate at Visit 3 and Visit 4).
- X. Screening procedures may begin as soon as informed consent is obtained and after the patient is diagnosed with a VTE requiring at least 3 months of treatment with anticoagulants including an initial parenteral treatment course of at minimum 5 to 7 days (but not longer than 21 days). Screening procedures may take place at different time points during the screening window. Screening laboratory tests are to be collected early enough during the screening window to ensure that results are received and reviewed by Visit 2 and that there is enough time for retesting, if needed. In case pre-treatment with VKAs has been initiated during the screening period, a local INR measurement should be performed at Visit 2 to confirm eligibility (INR < 2.0)
- Y. Visit 5 should be performed at least 3 days (6 consecutive dabigatran etexilate doses are taken) after Visit 4.

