1. INTRODUCTION

1.1 MEDICAL BACKGROUND

In contrast to adults, venous thromboembolism (VTE) in children is a rare event with an overall annual incidence of approximately 0.07-0.14 events per 10,000 children ([R06-2301](#)). Nevertheless it represents a significant management dilemma that requires therapeutic intervention ([R06-2301](#), [R06-2150](#), [R07-2959](#)).

The most common etiologic factor for VTE in children is the presence of a central venous line (CVL) ([R06-2305](#), [R06-2150](#)). Immediate complications of VTE include death from pulmonary embolism (PE) and non-lethal PE. Long-term complications involve recurrent VTE, post-thrombotic syndrome (PTS), and bleeding associated with anticoagulation therapy ([R07-2959](#), [R07-2954](#), [R07-2962](#), [R06-2305](#)).

The recommendations on antithrombotic therapy in children are based on extrapolation of adult data from randomized controlled studies or on small randomized or non-controlled studies in children ([P98-11480](#), [R07-2940](#)). The current standard of care (SOC) for the treatment of VTE in children is unfractionated heparin (UFH) or low molecular weight heparin (LMWH) administered for generally 5 to 7 days followed by 3 to 6 months of LMWH or vitamin K antagonists (VKA) ([R07-2939](#)).

There are frequent challenges with the use of UFH and OAC in children ([P06-06652](#), [R07-2938](#), [R07-2956](#)). For UFH, these include variable pharmacokinetics, need for venous access for both administration and monitoring and heparin-induced thrombocytopenia. For VKA, problematic issues with dosing include the significant influences of age, diet, medications and underlying diseases, which result in a need for frequent monitoring ([R07-2964](#)). Low molecular weight heparin has several potential advantages in children over UFH / VKAs for the treatment of VTE, which has prompted it becoming the preferred product in children despite the lack of adequate and well-controlled clinical trials. However, the use of LMWH requires subcutaneous administration with a needle poke causing pain in the child and anxiety for the parent or guardian which may translate into non-compliance. These problems with conventional anticoagulation provide the rationale for investigations of novel anticoagulants.

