3.3.3 Exclusion criteria

- 1) Conditions associated with an increased risk of bleeding:
 - a) Any prior intracranial haemorrhage, classified as a macrobleed¹. Any intracranial anatomical abnormality or intracranial aneurysm. Active meningitis, encephalitis, or intracranial abscess at randomisation.
 - b) Intracranial or intraspinal surgeries within 6 months of Visit 2 or any other major surgery within 4 weeks of Visit 2. Major surgeries may include an invasive operation upon an organ within the cranium, chest, abdomen, pelvic cavity or any other procedure regarded as major surgery per investigator judgment. In general, in major surgery, a mesenchymal barrier is opened (pleural cavity, peritoneum, meninges). Removal or insertion of a central venous line is not considered a major surgery provided haemostasis is achieved after the procedure.
 - c) Any major planned procedure that might put the patient at an increased risk of a bleed per investigator judgment within 5 days prior to taking study medication.
 - d) History of intraocular, spinal, retroperitoneal or atraumatic intra-articular bleeding unless the causative factor has been permanently treated (e.g. by surgery).
 - e) Gastrointestinal haemorrhage within the past year prior to screening unless the cause has been permanently eliminated (e.g., by surgery).
 - f) History of gastroduodenal ulcer disease.

¹ Patients with asymptomatic petechial or microbleeds may be included into the study as per investigator's judgment. As a general recommendation, an intracranial microbleed is considered to be ≤ 0.5 cm in greatest diameter on gradient recalled echo (GRE), or T2* MRI sequences (criteria may vary depending on MRI

imaging modalities; [R15-2999](#)). Irrespective of size, any cerebral bleed that causes focal neurologic symptoms and/or signs does not constitute a microbleed. Further, any blood visualized on a CT should be classified as a macrobleed, which is an exclusion criterion for the trial.

² Short-term pre-treatment with VKAs is permitted if the INR has not yet reached a therapeutic level (i.e. the INR is still < 2.0). The duration of the initial parenteral therapy inclusive VKA treatment if applicable must not exceed 21 days.

- g) History of haemorrhagic disorder or bleeding diathesis (e.g. von Willebrand disease, haemophilia A or B or other hereditary bleeding disorder, history of spontaneous intra-articular bleeding, history of prolonged bleeding after surgery/intervention).

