4.1.2 Method of assigning patients to treatment groups

After obtaining signed informed consent and if applicable assent, patients should complete the screening (Visit 1) procedures and laboratory assessments. Inclusion and exclusion criteria should be assessed to ensure inclusion of eligible patients.

Eligible patients who meet all inclusion and exclusion criteria will be randomly assigned to receive either dabigatran or standard of care (LMWH or VKA or fondaparinux) in an open-label fashion based on a 2:1 ratio (dabigatran:SOC). In addition, patients assigned to dabigatran etexilate OLF will be randomized based on 1:1 ratio to receive flavoured or unflavoured solvent for reconstitution. The intended SOC treatment must be specified at randomization. Patient assignment to the treatment groups will be managed by IRT. Access to the randomisation code will be controlled and documented. All necessary instructions for using the IRT system will be described in a user guide/manual, a copy of which will be available in the ISF. In this trial, IRT will be used for randomization, to track medication assignments, to monitor the appropriate age stratification according to strata 1, 2 and 3 and the minimum number of patients required in each age group. The IRT will also be used to control aspects of the medication supply chain.

Randomization will be initiated in stratum 1 and progressively open to stratum 2 and then 3 once the DMC authorizes the start of recruitment in strata 2 and 3 following the review of ongoing data in stratum 1 (considering patients from this trial and from the secondary VTE

Proprietary confidential information.

© 2019 Boehringer Ingelheim International GmbH or one or more of its affiliated companies. All rights reserved.

This document may not - in full or in part - be passed on, reproduced, published or otherwise used without prior written permission.

prevention trial 1160.108), data from previously completed phase IIa studies and any other relevant information as described in the DMC charter.

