5. VARIABLES AND THEIR ASSESSMENT

5.1 EFFICACY - PHARMACODYNAMICS

5.1.1 Endpoints of efficacy

Primary endpoint:

Efficacy combined endpoint Proportion of patients with:

- Complete thrombus resolution and;
- Freedom from recurrent VTE (including symptomatic and asymptomatic, contiguous progression or non-contiguous new thrombus, deep vein thrombosis, pulmonary and paradoxical embolism, thrombus progression) and;
- Freedom from mortality related to VTE.

The events outlined in the above combined primary endpoint will be assessed by radiologists or other such qualified clinicians using an appropriate method such as ultrasound, echocardiography, venography or computed tomography (CT scan) based on the location of the thrombus and the test used to perform the baseline assessment.

All components of the primary efficacy endpoint as well as all bleeding and all fatal events will be centrally adjudicated by an independent blinded committee.

Secondary endpoints:

- Freedom from major bleeding events (MBEs), defined as either fatal bleeding; clinically overt bleeding associated with a decrease in haemoglobin of at least 20 g/L in a 24-hour period; bleeding that is retroperitoneal, pulmonary, intracranial or otherwise involves the central nervous system; or bleeding that requires intervention in an operating suite.
- Pharmacokinetic and pharmacodynamic assessments at visit 3 (after at least six consecutive dabigatran doses) and after at least 3 days following any dabigatran dose adjustment
- Frequency of dose adjustments (i.e. Number of subjects with dose adjustment), temporary and permanent discontinuation from therapy and number of subjects with laboratory monitoring requirements for dose adjustment during the treatment phase
- Frequency of switch of type of anti-coagulation therapy (including dabigatran to SOC) (Frequency of subjects switching the type of anti-coagulation therapy including dabigatran etexilate to standard of care and switching from an intended standard of care treatment to another)
- Freedom from thrombus progression at end of therapy (day 84 after randomisation (Visit 8) or eEOT whichever comes first) compared to baseline
- Assessment of the acceptability of an age-appropriate formulation at end of therapy
- All bleeding events

Proprietary confidential information.

© 2019 Boehringer Ingelheim International GmbH or one or more of its affiliated companies. All rights reserved.

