5.2.2 Secondary endpoints

The secondary endpoints are:

- Freedom from major bleeding events (MBEs), defined as either fatal bleeding; clinically overt bleeding associated with a decrease in haemoglobin of at least 20 g/L in a 24-hour period; bleeding that is retroperitoneal, pulmonary, intracranial, or otherwise involves the central nervous system; or bleeding that requires intervention in an operating suite.
- Pharmacokinetic (PK) and pharmacodynamics (PD) assessments at Visit 3 (after at least six consecutive dabigatran etexilate (DE) doses) and after at least 3 days following any DE dose adjustment
- Frequency of dose adjustments (i.e. number of patients with dose adjustment) temporary and permanent discontinuation from therapy (and number of patients with laboratory monitoring requirements for dose adjustment during the treatment phase
- Frequency of switch of type of anti-coagulation therapy (including DE to standard of care (SOC)) (Frequency of patients switching the type of anti-coagulation therapy including DE to SOC and switching from an intended SOC treatment to another)
- Freedom from thrombus progression at end of therapy (day 84 after randomisation or eEOT, whichever comes first) compared to baseline (i.e. proportion of patients free from thrombus progression at end of therapy compared to baseline)
- Assessment of the acceptability of an age-appropriate formulation at end of therapy
- All bleeding events (i.e. proportion of patients with all bleeding events)
- All-cause mortality (i.e. proportion of patients with all-cause mortality)

- All components of the primary efficacy endpoints, including the proportion of patients with complete thrombus resolution, proportion of patients free from recurrent VTE, and proportion of patients free from VTE related death.

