PK parameters: All concentrations will be listed and summarized descriptively. The concentrations will be compared descriptively with the exposure observed in adult patients or healthy subjects previously. PK data from this study along with data from other trials in the dabigatran program will be used to further refine the adult population PK model (7), allowing it to be used for the generation of predictions optimized for paediatric populations. The results of this model refinement will be reported separately.

PD parameters: The following descriptive statistics will be calculated for the PD parameters aPTT, ECT and any additional PD assay: these include, but are not limited to N, arithmetic mean, standard deviation, minimum, median, and maximum. Further, ratios to baseline (i.e. visit 2) for these parameters will be calculated and assessed by descriptive statistics. Dabigatran concentrations derived from dTT will be compared to dabigatran concentrations determined by HPLC-MS/MS. The comparison will be reported separately.

Dose adjustments, switch of therapy, and discontinuation of medication

The number and percentage of patients with dose adjustments (up-titration and down-titration separately), temporary and permanent discontinuation from therapy, and laboratory monitoring requirements for dose adjustment during the treatment phase will be summarized descriptively by treatment arm on treated set. For the DE arm, dose adjustments until the switch of therapy to SOC will be considered.

The number of laboratory monitoring requirements per patient for dose adjustment during treatment phase will be summarised by the number and percentage of patients requiring 1, 2, or more lab monitoring, as well as the mean, SD, min, median, and max of the number of lab monitoring requirements per patient. For the DE arm, lab monitoring requirements prior to the first switch, if any, to SOC will be counted only.

Frequency of patients switching the type of anti-coagulation therapy, including DE to SOC or change from one type of SOC to another (LMWH, VKA, and Fondaparinux) will be provided descriptively by treatment arm on treated set. For the DE arm, only the switch from DE to SOC will be counted, while for the SOC arm, all switches among SOC medication types will be counted. Reasons for switch of therapy from DE to SOC and among SOC types will be summarized. Frequency of DE treated patients with changes in dose and/or formulation type will also be summarized.

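### SAP 7.5.2 counts every change of SOC type as a switch, not only departures from the SOC intended at randomisation, so a planned move onto a VKA can be counted and a real departure missed

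*SAP*

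**What the plan says.** **Endpoint.** Protocol 5.1.1 (and the synopsis) lists the frequency of patients who change their type of anticoagulation. It names two forms: dabigatran to SOC, and "switching from an intended standard of care treatment to another". SAP 5.2.2 repeats this: "switching from an intended SOC treatment to another".

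**Reference point.** Protocol 4.1.2 fixes what was intended: "The intended SOC treatment must be specified at randomization". Protocol 4.1.4 allows the SOC type to be changed later if necessary and does not treat that as stopping study medication.

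**Counting rule.** SAP 7.5.2 sets one rule per arm. The SOC rule is broad: "while for the SOC arm, all switches among SOC medication types will be counted". The types are LMWH, VKA and fondaparinux. In the dabigatran arm, a patient counts only on moving to SOC. The summary is descriptive, by arm, on the treated set, and reasons for switching are tabulated.

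**VKA status at entry.** Under footnote 2 in protocol 3.3.3, "Short-term pre-treatment with VKAs is permitted if the INR has not yet reached a therapeutic level", that is, an INR still below 2.0. Flow Chart footnote X and protocol 4.1.4 call for this to be checked locally at Visit 2.

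**The concern.** The definition asks whether the child left the SOC that was planned. The counting rule asks whether the recorded SOC type ever changed. The two questions can have different answers.

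LMWH is where they part. It is one of the initial parenteral drugs and also a named SOC type. A child whose intended SOC is a VKA enters with an INR below 2.0 if pre-treated, or has yet to start the VKA. If LMWH given after randomisation is entered as SOC, the later move onto the VKA is a type change under 7.5.2, although the child is moving to the intended drug. Conversely, a child intended for a VKA who receives only LMWH shows no type change and is not counted.

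At stake is how a named secondary endpoint is reported. Ease of use relative to LMWH and VKA is part of the rationale in protocol 2.1, so a SOC switch frequency that mixes planned moves with real departures could be misread. The trial is open-label and only the adjudication committee is blinded (protocol 4.1.5.1). If the rule is left as it stands, people who know the arm will decide how such moves are coded.

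**Working it through.** The documents give no expected switch rate, and no sample size or power for this endpoint, so there is no stated figure to reproduce. The check has two parts.

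**1. Definition against rule, by pattern of treatment**

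| SOC child | Counted under SAP 7.5.2? | Departure from intended SOC? |
|---|---|---|
| VKA intended; LMWH after randomisation recorded as SOC; then VKA | Yes | No |
| VKA intended; LMWH recorded as SOC throughout | No | Yes |
| VKA intended; any LMWH cover not recorded as SOC; then VKA | No | No |
| LMWH intended; LMWH, then VKA | Yes | Yes |

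Rule and definition disagree in the first two rows, in opposite directions. Whether a child falls in the first row or the third depends on how LMWH after Visit 2 is recorded, which the documents do not say.

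**2. Illustrative size of the first error**

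Inputs:
- n = 47 SOC children (protocol synopsis and 7.6). Protocol 3.3 treats anyone with at least one dose as evaluable, so this approximates the SOC part of the treated set.
- s = true share departing from the intended SOC. Not given; assumed 5% or 10%.
- v = share with a VKA as intended SOC. Not given; assumed 10% to 50%.
- b = share of those whose LMWH after randomisation is recorded as SOC before the VKA. Not given; assumed 0% to 100%.

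If every true departure is caught, counted rate = s + (1 − s) × v × b. The excess, (1 − s) × v × b, is zero when b = 0 and can never exceed v.

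| v | b | Counted, s = 5% | Counted, s = 10% |
|---|---|---|---|
| any | 0% | 5.0% (2.4 of 47) | 10.0% (4.7 of 47) |
| 10% | 50% | 9.8% (4.6) | 14.5% (6.8) |
| 30% | 50% | 19.3% (9.0) | 23.5% (11.0) |
| 30% | 100% | 33.5% (15.7) | 37.0% (17.4) |
| 50% | 100% | 52.5% (24.7) | 55.0% (25.9) |

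Example: s = 5%, v = 30%, b = 50% gives 0.05 + 0.95 × 0.30 × 0.50 = 0.1925, and 47 × 0.1925 = 9.0 children.

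The second error works the other way. Each child who never takes the intended SOC and so shows no type change lowers the counted rate by 1/47 = 2.1 percentage points. With b = 0 and any such child, the rule undercounts.

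If only departures from the intended SOC are counted, the rate equals s (2.4 or 4.7 of 47 here), whatever v and b are.

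**The case against.** **The definition may be broad enough.** The endpoint says that switching includes the two named forms, so both could be examples of a general idea, any change of type, and 7.5.2 would then follow that idea. The wording allows this. But it leaves the specific reference to an intended SOC, and its capture at randomisation, with no role in the count.

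**The mechanism is not documented.** This stands. Nothing describes LMWH cover after randomisation in the SOC arm, says it would be recorded as a SOC type, or says that stopping LMWH while a VKA continues is a change of type. Initial parenteral therapy is treated as a separate phase, documented at screening (protocol 4.2) and reported at baseline (SAP 7.1). The effect may therefore be nil. LMWH is also described as the preferred paediatric agent (protocol 1.1 and 2.1), so a high VKA share should not be presumed.

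**Planned moves can be identified.** SAP 7.5.2 tabulates reasons for switching and SAP 7.7 lists SOC type, dates, change and reason for each patient. That helps a careful reader but does not correct the headline SOC frequency, and it does not recover children who never took the intended type.

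**A stronger reading.** A reader might infer that the rule does inflate the SOC rate by about the VKA-intended share and makes dabigatran look more stable than it is. The documents do not support that. The first part assumes all such children have LMWH recorded as SOC, and it ignores missed departures. The second is wrong for the dabigatran count: dabigatran is a single type, so a change to SOC is the only first switch available, and later SOC changes would not alter a per-patient frequency. At most, the SOC arm could look less stable by comparison.

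**Limited consequence.** The endpoint is descriptive and untested, and no claim is attached to it. This stands.

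**Conclusion.** The point holds as a mismatch between a definition and its counting rule. Followed literally, SAP 7.5.2 counts a recorded move from LMWH onto the intended VKA and misses a child who never takes the intended SOC. It can therefore raise, and in the second case lower, the descriptive SOC switch frequency relative to departures from the intended SOC.

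The size is unknown. The upward error runs from zero to the VKA-intended share of about 47 children; the tabulated rates illustrate assumed inputs and are not estimates. The conclusion rests on reading the intended-SOC wording as the operative reference for the SOC arm. The upward error also requires LMWH after randomisation to be recorded as a SOC type. The dabigatran count and the primary analysis are unaffected. The correction is worth making because it costs little and the outcome otherwise turns on an unstated recording convention, but no confirmatory result depends on it.

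**What to change.** In SAP 7.5.2:
- count a SOC patient as switching only when the SOC type taken departs from the type specified at randomisation, including when the specified type is never taken;
- do not count a move onto that specified type;
- tabulate moves onto the intended type, and any other type changes, separately.

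No INR-based rule for the end of parenteral cover is needed. It would require a therapeutic threshold for each patient, and protocol 4.1.3 leaves INR targets to local guidelines. The 2.0 cut-off is an entry criterion only.

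The cost is a short SAP edit and one extra table. The intended SOC is already recorded at randomisation, and SAP 7.7 already lists SOC type, dates and changes, so no new data should be needed. Treatment does not change.
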